#### Pregnancy

All initial reports of pregnancy must be reported to Janssen Scientific Affairs, LLC by the PRINCIPAL INVESTIGATOR **within 24 hours of becoming aware of the event** using the Serious Adverse Event Form. Abnormal pregnancy outcomes (e.g. spontaneous abortion, fetal death, stillbirth, congenital anomaly, ectopic pregnancy) are considered serious adverse events and must be reported using the Serious Adverse Event Form.

Any subject who becomes pregnant during the study must be promptly withdrawn from the study and discontinue further study treatment.

Because the effect of the Janssen medicinal product on sperm is unknown, pregnancies in partners of male subjects exposed to a Janssen medicinal product will be reported by the PRINCIPAL INVESTIGATOR **within 24 hours of their knowledge of the event** using the Serious Adverse Event Form. Depending on local legislation this may require prior consent of the partner.

Follow-up information regarding the outcome of the pregnancy and any postnatal sequelae in the infant will be required.

#### **5. Maintenance of Safety Information**

All safety data should be maintained in a clinical database in a retrievable format. The PRINCIPAL INVESTIGATOR shall provide all adverse events, both serious and non-serious, in report format. However, in certain circumstances more frequent provision of safety data may be necessary, e.g. to fulfill a regulatory request, and as such the data shall be made available within a reasonable timeframe at Janssen Scientific Affairs, LLC request.

#### **6. Procedures for Reporting Safety Data and Product Quality Complaints (POCs) for Janssen Medicinal Products to Janssen Scientific Affairs, LLC**

All adverse events and special situations, whether serious or non-serious, related or not related, following exposure to a Janssen medicinal product are to be documented by the investigator and recorded in the CRF and in the subject's source records. Investigators must record in the CRF their opinion concerning the relationship of the adverse event to a Janssen medicinal product.

All (serious and non-serious) adverse events reported for a Janssen medicinal product should be followed-up in accordance with clinical practice.

##### **6.1. SAEs and Special Reporting Situations**

All serious adverse events that have not resolved by the end of the study, or that have not resolved upon discontinuation of the subject's participation in the study, must be followed until any of the following occurs:

- The event resolves
- The event stabilizes
- The event returns to baseline, if a baseline value/status is available

- The event can be attributed to agents other than the study drug or to factors unrelated to study conduct
- It becomes unlikely that any additional information can be obtained (subject or health care practitioner refusal to provide additional information, lost to follow-up after demonstration of due diligence with follow-up efforts)

The PRINCIPAL INVESTIGATOR will transmit all SAEs and special situations following exposure to a Janssen product under study in a form provided by Janssen Scientific Affairs, LLC in accordance with Section 10, Transmission Methods, in English **within 24-hours of becoming aware of the event(s).**

In the event the study is blinded, the PRINCIPAL INVESTIGATOR will submit an unblinded SAE or pregnancy exposure report to Janssen Scientific Affairs, LLC.

All follow-up information for serious adverse events that are not resolved at the end of the study or by the time of patient withdrawal must be reported directly by the PRINCIPAL INVESTIGATOR, **within 24 hours becoming aware**, to Janssen Scientific Affairs, LLC using the Janssen Scientific Affairs, LLC Serious Adverse Event Report

All available clinical information relevant to the evaluation of a related SAE or special situation is required.

- The PRINCIPAL INVESTIGATOR is responsible for ensuring that these cases are complete and if not are promptly followed-up. A safety report is not considered complete until all clinical details needed to interpret the case are received. Reporting of follow-up information should follow the same timeline as initial reports.
- Copies of any and all relevant correspondences with regulatory authorities and ethics committees regarding any and all serious adverse events, irrespective of association with the Janssen Product under study, are to be provided to Janssen Scientific Affairs, LLC using a transmission method in Section 10 from this Exhibit within **24 hours of such report or correspondence being sent to applicable health authorities.**

#### **6.2. Non-Serious AEs**

All non-serious adverse events should be reported to Janssen Scientific Affairs, LLC according to the timeframe outlined in the Research Funding Agreement section entitled Reporting of Data.

#### **6.3. PQC Reporting**

A PQC may have an impact on the safety and efficacy of the product. Timely, accurate, and complete reporting and analysis of PQC information from studies are crucial for the protection of patients, investigators, and Janssen Scientific Affairs, LLC, and are mandated by regulatory agencies worldwide. Janssen Scientific Affairs, LLC has established procedures in conformity with regulatory requirements worldwide to ensure appropriate reporting of PQC information. Lot and/or Batch #'s shall be collected or any reports failure of expected pharmacological action (i.e., lack of effect). The product should be quarantined immediately and if possible, take a picture.

All initial PQCs involving a Janssen medicinal product under study must be reported to Janssen Scientific Affairs, LLC by the PRINCIPAL INVESTIGATOR **within 24 hours**

**after being made aware of the event.** The Janssen contact will provide additional information/form to be completed.

If the defect for a Janssen medicinal product under study is combined with either a serious adverse event or non-serious adverse event, the PRINCIPAL INVESTIGATOR must report the PQC to Janssen Scientific Affairs, LLC according to the serious adverse event reporting timelines. A sample of the suspected product should be maintained for further investigation if requested by Janssen Scientific Affairs, LLC.

**7. Reporting Procedures for Reporting Safety Data and Product Quality Complaints (PQCs) for Non-Janssen Medicinal Products**

For SAEs, special reporting situations and PQCs following exposure to a non-Janssen medicinal product under study, the PRINCIPAL INVESTIGATOR should notify the appropriate regulatory/competent authority or the manufacturer of that medicinal product (in the absence of appropriate local legislation) as soon as possible.

**8. Transmission Methods**

The following methods are acceptable for transmission of safety information to Janssen Scientific Affairs, LLC:

- Electronically via Janssen SECURE Email service (preferred)
- For business continuity purposes, if SECURE Email is non-functional:
  - Facsimile (fax), receipt of which is evidenced in a successful fax transmission report
- Telephone (if fax is non-functional).

Please use the contact information and process information provided by Janssen Scientific Affairs, LLC.

## 11.0 Treatment Evaluation

The International Myeloma Working Group (IMWG) uniform response criteria will be used to assess response to therapy.

### 11.1 Terms and definitions

- **M-protein:** synonyms include M-spike, monoclonal protein and myeloma protein, paraprotein, M-component.

Serum M-protein level is quantitated using densitometry on SPEP except in cases where the SPEP is felt to be unreliable.

- M-proteins migrating in the  $\beta$ -region (usually IgA M-proteins)
- Cases in which the M-protein is so large and narrow on agarose (some specimens  $>4$  g/dL) that they underestimate the actual immunoglobulin level (by greater than 1500 mg/dL) due to technical staining properties of the agarose gel.
- Cases in which there are multiple peaks of same M-protein (aggregates or dimers)

If SPEP is not available or felt to be unreliable (above examples) for routine M-protein quantitation, then quantitative immunoglobulin levels derived from nephelometry or turbidometry can be accepted, with the exception that quantitative IgG may not be used. However, this must be explicitly reported at baseline, and only nephelometry can be used for that patient to assess response. SPEP derived M-protein values and quantitative nephelometric immunoglobulin values cannot be used interchangeably.

Urine M-protein measurement is estimated using 24-h UPEP only. Random or 24 h urine tests measuring kappa and lambda light chain levels are not reliable and are not recommended.

**FLC estimation** is currently carried out using the serum FLC assay (Freelite, The Binding Site Limited, UK). Patients with kappa/lambda FLC ratio  $<0.26$  are defined as having monoclonal lambda FLC and those with ratios  $>1.65$  as having a monoclonal kappa FLC. The monoclonal light chain isotype is considered the involved FLC isotype, and the opposite light chain type as the uninvolved FLC type.

- **Response terms:** The following response terms will be used: stringent Complete Response (sCR), complete response (CR), very good partial response (VGPR), partial response (PR), Minimal Response (MR), stable disease (SD), and progressive disease (PD).

In addition, for each response category, there will be an “unconfirmed” response category, which will be for internal use, for the purpose of guiding decision making and test ordering. These designations will be applied at the time of the first measurement at which the quantitative aspect of the response category has been satisfied without the confirmation step having been satisfied. The designation “u” will precede the standard abbreviations, and will include usCR, uCR, uVGPR, uPR, uMR, uPD.

- **Measurable disease:** Patients who have a measurable serum or urine M-protein.

- Serum M-protein  $\geq 1$  g/dl  
NOTE: Quantitative IgG may not be used for defining measurable disease
- Urine M-protein  $\geq 200$  mg/24 h
- Serum FLC assay: Involved FLC level  $\geq 10$  mg/dl provided serum FLC ratio is abnormal
- Bone marrow plasma cells  $\geq 30\%$

The serum free light chain (FLC) assay is of particular use in monitoring response to therapy in patients who have oligo-secretory or non-secretory disease and **should be used in assessing response only if the baseline serum and/or urine M proteins are not “measurable” as above, and the baseline level of the involved FLC is “measurable.”** When using this assay, it is important to note that the FLC levels vary considerably with changes in renal function and in patients with renal insufficiency, the levels of both the kappa and lambda may remain elevated, but the ratio normalizes with achievement of CR. Thus, both the level of the involved and the uninvolved FLC isotype (i.e., the involved/uninvolved ratio or involved-uninvolved difference) should be considered in assessing response. ***Patients included on the study on the basis of FLC alone (i.e., no measurable serum/urine M-protein) should be the only ones who are evaluated using FLC response criteria. The others should follow usual criteria and ignore FLC results with the exception of defining stringent complete response.***

- **Evaluable disease:** Patients who do not have a “measurable” serum M-protein, serum free light chain, or urine M-protein.
- **Oligosecretory myeloma:** Patient with multiple myeloma who has NEVER had “measurable” serum M-protein or urine M-protein, but has had a detectable M-protein in his/her serum and/or urine and/or measurable serum free light chain.
- **Non-secretory myeloma:** Patient with multiple myeloma who has NEVER had a detectable M-protein in his/her serum and/or urine.

## 11.2 Clarification of test indications

Listed below are the minimal required tests required to assess response based on the characteristics of their disease at on study.

Table 11.2				
Tests Required To Assess Response (Must Be Done At Each Disease Measurement Visit except as indicated  )				
On Study Baseline Value	SPEP 	24 hr UPEP 	Ig FLC	BM Bx
Serum M-protein $\geq$ 1 g/dl, and urine M-protein $\geq$ 200 mg/24 hrs	X	X		
Serum M-protein $\geq$ 1 g/dl, but urine M-protein < 200 mg/24 hrs	X			
Serum M-protein <1 g/dl, and urine M-protein $\geq$ 200 mg/24 hrs		X		
Serum M-protein < 1 g/dl, urine M-protein < 200 mg/24 hrs, but involved Ig FLC is $\geq$ 10 mg/dL			X	
Serum M-protein < 1 g/dl, urine M-protein < 200 mg/24 hrs, involved Ig FLC is <10 mg/dL, bone marrow $\geq$ 30% plasma cells				X 

 *SPEP, UPEP, Immunofixation studies of both serum and urine, and Bone marrow biopsy are required to document CR regardless of registration values, and in addition FLC measurement and bone marrow immunophenotyping is required to document sCR. SPEP and UPEP are required to document VGPR regardless of registration values.*

 *For serum measurable patients, 24 hour urine does not need to be confirmed (i.e. repeated after documented response) for any response category*

 *At a minimum, a bone marrow biopsy should be repeated every 3 months until documented response. Bone marrow biopsy results do not need to be repeated after documented response.*

 *If serum M-protein is being followed by quantitative immunoglobulin levels derived from nephelometry or turbidometry, quantitative immunoglobulins are required. SPEP is only required to document CR or VGPR.*

## 11.3 Confirmed response

In order to be classified as a hematologic response, confirmation of serum M- protein, serum immunoglobulin free light chain (when primary determinant of response) and urine M- protein (when primary determinant of response) results must be made by verification on two consecutive determinations.

- Bone marrow aspirate and biopsy are **only** required to document CR or sCR, except for patients with evaluable disease **only**, where a bone marrow is required to document all response categories including progression. However, a second confirmatory bone marrow is **not** required to confirm response in any case.
- Radiographic studies are not required to satisfy these response requirements; however, if radiographic studies were performed there should be no evidence of progressive or new bone lesions.

Appropriate tests required to document and confirm response are listed in Table 11.2

#### 11.4 Bone progression

Caution must be exercised to avoid rating progression on the basis of variation of radiologic technique alone. Compression fracture does not exclude continued response and may not indicate progression. When progression is based on skeletal disease alone, it should be discussed with the Study Chair before removing the patient from the study.

#### 11.5 Response and Progression

Criteria for response and progression are listed in Table 11.5. Progressive disease for all patients as defined in Table 11.5.

Table 11.5

IMWG MRD NEGATIVITY CATEGORY	RESPONSE CRITERIA a
Sustained MRD	MRD negativity in the marrow (NGF or NGS, or both) and by imaging as defined below, confirmed minimum of 1 year apart. Subsequent evaluations can be used to further specify the duration of negativity (eg, MRD-negative at 5 years)
Flow MRD k	Absence of phenotypically aberrant clonal plasma cells by NGF on bone marrow aspirates using the EuroFlow standard operation procedure for MRD detection in multiple myeloma (or validated equivalent method) with a minimum sensitivity of 1 in $10^5$ nucleated cells or higher
Sequencing MRD k	Absence of clonal plasma cells by NGS on bone marrow aspirates in which presence of a clone is defined as less than two identical sequencing reads obtained after DNA sequencing of bone marrow aspirates using the LymphoSIGHT platform (or validated equivalent method) with a minimum sensitivity of 1 in $10^5$ nucleated cells or higher
Imaging Plus MRD k	MRD negativity as defined by NGF or NGS plus disappearance of every area of increased tracer uptake found at baseline or a preceding PET/CT or decrease to less than mediastinal blood pool SUV or decrease to less than that of surrounding normal tissue
STANDARD IMWG RESPONSE CATEGORY	RESPONSE CRITERIA a
Stringent Complete Response (sCR) b	CR as defined plus Normal FLC ratio and 

• Absence of clonal PCs by immunohistochemistry or 2- to 4- color flow cytometry i

Complete Response (CR) b	

• Negative immunofixation of serum and urine c and

• Disappearance of any soft tissue plasmacytoma and

• <5% PCs in Bone Marrow and

• If the only measurable disease is FLC, a normal FLC ratio d

Very Good Partial Response (VGPR)	
 
Serum and urine M-protein detectable by immunofixation but not on electrophoresis c or
 
≥90% reduction in serum M-protein and urine M-protein <100 mg/24 hc
 
If the only measurable disease is FLC, a >90% reduction in the difference between involved and uninvolved FLC levels
 

Partial Response (PR)	
 
If present at baseline, ≥ 50% reduction of serum M-protein and reduction in 24-hour urinary M-protein by ≥90% or to <200 mg/24hrsc
 
If the only measurable disease is FLC, a ≥50% reduction in the difference between involved and uninvolved FLC levels
 
If the only measurable disease is BM, a ≥ 50% reduction in BM PCs (provided the baseline PCs was ≥ 30%)
 
If present at baseline, ≥ 50% reduction in the size (SPD) of soft tissue plasmacytomasj
 

Minimal Response (MR)	
 
If present at baseline, ≥25% but ≤ 49% reduction of serum M protein and reduction in 24-hour urine M-protein by 50-89% which still exceeds 200mg/24 hoursc and
 
If present at baseline, ≥50% reduction in the size (SPD) of soft tissue plasmacytomaj
 

Stable Disease (SD)	
 
Not meeting criteria for sCR, CR, VGPR, PR, MR or PD
 

Progressive Disease (PD) b, h	
Increase of 25% from lowest value in any of the following f, g:
 
 
Serum M-protein (absolute increase must be ≥ 0.5 g/dL) and/or
 
Urine M-protein (absolute increase must be ≥ 200 mg/24 hrs) and/or
 
If the only measurable disease is FLC, the difference between involved and uninvolved FLC levels (absolute increase must be >10 mg/dL) and/or
 
If the only measurable disease is BM, bone marrow PC percentage (absolute increase must be ≥ 10%)e
 
 
Or any one or more of the following:
 
 
Development of new bone lesion or soft tissue plasmacytoma or ≥50% increase from nadir in the size (SPD) of existing bone lesions or soft tissue plasmacytoma or ≥ 50% increase in the longest diameter of a previous lesion >1 cm in short axisj
 
50% increase in circulating plasma cells (minimum of 200 cells per L) if this is the only measure of disease
 

Clinical Relapse	
One or more of the following direct indicators of increasing disease and/or end-organ dysfunction that are considered related to the underlying plasma cell proliferative disorder:
 
 
Development of new soft tissue plasmacytomas or bone lesions on skeletal survey, magnetic resonance imaging, or other imaging
 
Definite increase in the size of existing plasmacytomas or bone lesions. A definite increase is defined as a 50% (and at least 1 cm) increase as measured serially by the sum of the products of the cross-diameters of the measurable lesion
 
Hypercalcemia (>11.5 mg/dL; >2.875mM/L)
 
Decrease in hemoglobin of more than 2 g/dL (1.25mM) or to less than 10 g/dL
 
Rise in serum creatinine by more than or equal to 2 mg/dL
 

	( $\geq 177 \text{mM/L}$ ) 6. Hyperviscosity
--	---

a All response categories require two consecutive assessments (sCR, CR, VGPR, PR, MR, PD) made at any time before the institution of any new therapy. MRD tests should be initiated only at the time of suspected complete response. sCR, CR, VGPR, PR, MR and SD categories and MRD require no known evidence of progressive or new bone lesions or extramedullary plasmacytomas if radiographic studies were performed. However, radiographic studies are not required to satisfy these response requirements except for the requirement of FDG PET if imaging MRD-negative status is reported. Bone marrow assessments need not be confirmed. Each category, except for stable disease, will have a working subcategory of "unconfirmed" [prefix 'u'] to designate first time point at which response category MAY have been achieved if confirmed. The date of the initial test is considered as the date of response for evaluation of time dependent outcomes such as duration of response.

b CR patient will need to progress at the same level as VGPR and PR patients to be considered a PD. A positive immunofixation alone is not sufficient.

c If more than one M protein spike meets the criteria for measurable disease at baseline, then both need to be followed for response. Otherwise, only follow the measurable M protein spike for response.

d In patients in whom the only measurable disease is by serum FLC levels: CR in such patients indicates a normal FLC ratio of 0.26-1.65 in addition to the CR criteria listed above.

e Bone marrow criteria for PD are only to be used in patients without measurable disease by M protein and by FLC;

f A "25% increase" refers to M protein, FLC and bone marrow results and does not refer to bone lesions, soft tissue plasmacytoma or hypercalcemia. The lowest value does not need to be a confirmed value. If the lowest serum M-protein is  $\geq 5 \text{ g/dL}$ , an increase in serum M-protein of  $\geq 1 \text{ g/dL}$  is sufficient to define disease progression.

g In the case where a value is felt to be a spurious result per physician discretion (for example, a possible lab error), that value will not be considered when determining the lowest value.

h Progressive disease should be confirmed on two consecutive evaluations, where the timing of confirmation is per the treating physician and can be done immediately within the same cycle or on the next cycle. However, treatment may be discontinued for progressive disease that is unconfirmed per physician discretion. In this case, an objective status of PD should be entered on the measurement form and progressive disease should be reported on the event monitoring form.

i Presence/absence of clonal cells is based upon the k/l ratio. An abnormal k/l ratio by immunohistochemistry requires a minimum of 100 plasma cells for analysis. An abnormal ratio reflecting presence of an abnormal clone is k/l of 4:1 or 1:2.

j Plasmacytoma measurements should be taken from the CT portion of the PET/CT, or MRI scans, or dedicated CT scans where applicable. For patients with only skin involvement, skin lesions should be measured with a ruler. Measurement of tumor size will be determined by the sum of the products of the maximal perpendicular diameters of measured lesions (SPD).

k Requires a complete response as defined in the table. MRD tests should be initiated only at the time of suspected complete response. MRD requires no known evidence of progressive or new bone lesions if radiographic studies were performed. However, radiographic studies are not required to satisfy these response requirements except for the requirement of FDG PET if imaging MRD-negative status is reported.

**NOTE: Interference with Determination of Complete Response:** Daratumumab is a human IgG kappa monoclonal antibody that can be detected on both, the serum protein electrophoresis (SPE) and immunofixation (IFE) assays used for the clinical monitoring of endogenous M-protein. This interference can impact the determination of complete response and of disease progression in some patients with IgG kappa myeloma protein.

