#### 4.0 Test Schedule

##### 4.1 Schedule of assessments

	Days Prior to Registration		Every 14 days (cycles 1 - 3) 	Every cycle, Induction 	Maintenance Phase: (every cycle) 
	≤30 days	≤14 days			
Complete medical history	X				
Adverse Event monitoring		X		X	X 
Physical exam, weight and vital signs		X		X	X 
Height		X			
Performance status (ECOG scale)		X		X	X 
CBC with diff.		X	X	X	X 
Prothrombin time (PT)	X				
Blood type and screen	X				
Chemistry group to include sodium, potassium, glucose, alkaline phosphatase; Total and Direct bilirubin; SGOT (AST);ALT serum creatinine, calcium		X	X	X	X 
sTSH, T3, T4	X				
LDH, Beta 2 -microglobulin, C-reactive protein	X				
Viral hepatitis panel including HBsAg, HB core antibody, and HB antibody	X 			X 	X 
Electrophoresis of serum and urine		X		X 	X 
Affected Immunoglobulin		X		X 	X 
Immunofixation serum and urine	X			X 	X 
Immunoglobulin free light chain		X		X 	X 
X-ray skeletal survey or WBLDCT	X			X 	X 
Bone marrow aspirate and biopsy	X			X 	X 
Research bone marrow and blood sample R,12	X			X 	X
Chest x-ray	X				

	Days Prior to Registration		Every 14 days (cycles 1 - 3) 	Every cycle, Induction 	Maintenance Phase:
	≤30 days	≤14 days			(every cycle) 
Serum pregnancy test		X 			
Patient Medication Diary (Appendix V) 				X	X
QOL questionnaire (Appendix VII)		X		X 	X 

- 1) All scheduled visits will have a window of  $\pm$  4 days unless otherwise stated
- 2) Immunofixation (IF) needed only in the absence of M-spike to document CR or sCR.

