- 3) For women of childbearing potential only. Must be done  $\leq$  7 days prior to registration. Pregnancy tests for females of childbearing potential. A female of childbearing potential (FCBP) is a sexually mature female who: 1) has not undergone a hysterectomy or bilateral oophorectomy; or 2) has not been naturally postmenopausal for at least 24 consecutive months (i.e., has had menses at any time in the preceding 24 consecutive months). Pregnancy tests must occur within 10 – 14 days and again within 24 hours prior to prescribing lenalidomide for cycle 1. FCBP with regular or no menstruation must have a pregnancy test weekly for the first 4 weeks and then every 28 days while on therapy (including breaks in therapy); at discontinuation of lenalidomide and at Day 28 post the last dose of lenalidomide. Females with irregular menstruation must have a pregnancy test weekly for the first 4 weeks and then every 14 days while on therapy (including breaks in therapy), at discontinuation of lenalidomide and at Day 14 and Day 28 post the last dose of lenalidomide (see Appendix VI: Risks of Fetal Exposure, Pregnancy Testing Guidelines and Acceptable Birth Control Methods) potential only.
- 4) WBLDCT-whole body low dose CT, Every 12 cycles or if clinically indicated.
- 5) FLC is required only if used to assess disease response during active phase
- 6) At the end of 4 cycles, 12 cycles, after 12 and 24 cycles of maintenance (Cycles 24 and 36) and to document CR or disease progression.
- 7) The diary must begin the day the patient starts taking the medication and must be completed per protocol and returned to the treating institution.
- 8) Affected immunoglobulin refers to the baseline M-protein type, that is, IgG, IgA, IgD, or IgM. Not applicable if patient “non-secretory” or if patient has no heavy chain, i.e. light chain myeloma. Affected immunoglobulin is required after baseline only if it used for disease monitoring instead of SPEP (for e.g. IgA myeloma)
- 9) The QOL questionnaire will be filled out by the patient at baseline, every cycle for the first 4 cycles, and then every 3 cycles.
- 10) Urine Electrophoresis required only if used to assess disease response
- 11) Does not need to be repeated at Cycle 1 Day 1. Baseline values can be used for Cycle 1.
- 12) Not mandatory at baseline or disease progression

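### Read as written, a daratumumab-only band fails CR, so the primary CR rate can be understated in IgG-kappa patients, and no rule or sensitivity analysis deals with it

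*Combined protocol and SAP*

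**What the plan says.** - **Endpoint and rule.** Sections 16.11 and 16.311 define success as CR or sCR on two consecutive evaluations at least two weeks apart. Section 16.211 calls an arm promising at 13 or more successes in 36 and ineffective at 12 or fewer.
- **CR criterion.** The CR row of Table 11.5 requires "Negative immunofixation of serum and urine", together with under 5% marrow plasma cells and no soft tissue plasmacytoma.
- **Interference.** The note closing Section 11.5 says that daratumumab, an IgG kappa antibody, is detectable on both serum assays, and adds: "This interference can impact the determination of complete response and of disease progression in some patients with IgG kappa myeloma protein".
- **Exposure.** Section 7.1 gives daratumumab in every cycle of induction and maintenance in both arms, so no drug-free response assessment is planned.
- **When immunofixation is done.** Section 4.1 note 2 says "Immunofixation (IF) needed only in the absence of M-spike to document CR or sCR". Table 11.2 note 1 lists electrophoresis and immunofixation of serum and urine and ends "Bone marrow biopsy are required to document CR regardless of registration values".
- **Benchmark.** Section 16.21 cites a 27% CR rate with ixazomib, lenalidomide and dexamethasone, then sets 25% as ineffective and 45% as worth pursuing.

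**The concern.** The protocol names a test artefact that bears on its own primary endpoint, then gives no instruction for it. Sections 4.1, 11, 14 and 16 contain no assay that separates drug from disease, no scoring rule for a persistent IgG-kappa band, no adjudication step and no analysis by isotype.

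The nearby text does not fill the gap. Table 11.5 footnote c says "Otherwise, only follow the measurable M protein spike for response", which does not help when drug and disease share an isotype. Footnote g lets a physician discard a spurious result, but only so that "that value will not be considered when determining the lowest value", which concerns progression.

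What is at stake is the go/no-go count. A patient in true CR whose only remaining band is drug is recorded as a failure, and the benchmark regimen carried no such handicap. MRD negativity, an exploratory endpoint, inherits the problem because Table 11.5 footnote k makes CR a precondition. The note also mentions progression; this point is confined to CR.

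**Working it through.** **1. Reproduce the plan.** From Sections 16.21 to 16.22: n = 36, success if X ≥ 13, X binomial. P(X ≥ 13) is 0.092, 0.264, 0.507, 0.739 and 0.893 at true rates of 25, 30, 35, 40 and 45%. These agree with the tabulated 0.09, 0.26, 0.51, 0.74 and 0.89.

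**2. Downward case (criterion applied literally).** Let q be the IgG-kappa share of patients and m the share of their true CRs that show a drug band. Neither is in the documents; both are assumed. Reading 45% as the interference-free CR rate:

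- scored rate = 0.45 × (1 − q × m)
- CRs missed per arm = 36 × 0.45 × q × m

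| q | m | Scored rate | CRs missed | P(X ≥ 13) |
|---|---|---|---|---|
| 0.30 | 0.10 | 0.4365 | 0.49 | 0.860 |
| 0.30 | 0.50 | 0.3825 | 2.43 | 0.664 |
| 0.35 | 0.25 | 0.4106 | 1.42 | 0.779 |
| 0.40 | 0.10 | 0.4320 | 0.65 | 0.848 |
| 0.40 | 0.50 | 0.3600 | 3.24 | 0.557 |

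If 45% is instead the rate of CR as scored under the plan's own criteria, any masking is already inside it and power stays at 0.893.

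**3. Upward case (an assessor departs from the literal criterion).** Let u be the share of all true non-CRs counted as CR, also assumed. At a true rate of 25%:

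- scored rate = 0.25 + 0.75 × u
- extra CRs per arm = 36 × 0.75 × u

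For u = 0.02 the scored rate is 0.265, with 0.54 extra CRs and P(X ≥ 13) = 0.133. For u = 0.05 it is 0.2875, with 1.35 extra CRs and P(X ≥ 13) = 0.211.

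Only IgG-kappa patients can contribute. If they make up 30-40% of non-CRs, u = 0.02 to 0.05 means that 0.02/0.40 = 5% to 0.05/0.30 = 17% of IgG-kappa non-CRs are overcalled.

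**4. The two immunofixation instructions.** Section 4.1 note 2 makes immunofixation depend on there being no M-spike; Table 11.2 note 1 requires it for every CR. If a drug band on electrophoresis is taken for an M-spike, note 2 gives no prompt to run the test that the CR call needs.

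**The case against.** **The text does contain a default.** Any positive immunofixation is not CR. This stands, and it fixes the direction: as written, the bias is downward. A reader might infer that the CR rate is equally open to inflation. The documents do not support that. Section 11.1 lists terms for M-protein ("synonyms include M-spike, monoclonal protein and myeloma protein", among others) but does not authorise setting a band aside. An overcalled patient would also need a clean marrow, negative urine immunofixation and confirmation at a second evaluation.

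**Success is defined as objective status, so 45% may already mean CR as scored.** This also stands. The loss of power depends on the other reading of 45%, which the plan does not state.

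**The chance of landing on 12 or 13 does not measure interference.** A reader might quote it (0.12 at a true 25%, 0.27 at 35%, 0.13 at 45%) as the size of the problem. It describes any 13-of-36 rule and contains nothing about drug bands.

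**The CR work-up is not fully blocked by a drug spike.** Section 4.1 note 6 schedules marrow after cycles 4, 12, 24 and 36 "and to document CR or disease progression", and Table 11.2 note 1 still asks for immunofixation. The conflict can delay or omit the test; it does not make CR unreachable.

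**Section 11.0 adopts the IMWG criteria by reference.** That source cannot be consulted here, so the absence of a rule is established only for these documents.

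**No comparison between arms is planned.** The case therefore rests on each arm's own decision.

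**Conclusion.** The point holds in a limited form. The protocol acknowledges that daratumumab can affect the CR call in some IgG-kappa patients. Its literal criterion then scores a drug-only band as a failure, and nothing in the analysis plan shows how much of the result turns on that. The direct bias is downward; upward error needs a departure from the written criterion that no rule forbids.

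The size is unknown. On the assumed shares in the working, 0.5 to 3.2 CRs per arm are missed and the probability of reaching 13 falls from 0.89 to between 0.86 and 0.56, provided 45% is an interference-free rate. Overcalling 2-5% of all non-CRs would raise the type I error from 0.09 to between 0.13 and 0.21. A reader might infer that the trial is underpowered. The documents do not support that, because 0.89 stands if 45% means CR as scored. This should be fixed; confidence is medium because every magnitude rests on assumed inputs.

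**What to change.** 1. **Sections 4.1 note 2 and 11.2.** Reconcile the two instructions: an electrophoresis band that may be daratumumab does not remove the need for immunofixation when CR is otherwise suspected.
2. **Section 11.5.** State one scoring rule, identical for all sites and both arms and agreed in writing with the laboratory before results are seen. A band the laboratory has shown to be daratumumab is not M-protein; an unresolved band counts as not CR.
3. **Section 16.31.** Keep the 13-of-36 rule. Beside it, report the literal count in which any band fails. Also report a sensitivity count that adds IgG-kappa patients who meet every other CR criterion on two consecutive evaluations at least two weeks apart and whose only failing is a single IgG-kappa band consistent with daratumumab. Marrow need not be repeated.
4. **Reporting.** Give CR for IgG-kappa patients and for other isotypes.
5. **Status.** State that items 3 and 4 inform interpretation near 13 and do not override the rule. Label them post hoc for any arm already analysed.

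**Cost.** A few sentences, one paragraph and one table, with sample size and cut-off unchanged. Section 18.5 already collects the electrophoresis, immunofixation and marrow reports. Section 13.1 continues treatment for both CR and VGPR, so the scoring does not alter care.

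**Downsides.** A few extra immunofixations are needed. Where a band cannot be resolved, the primary count keeps the literal downward bias. The sensitivity count may include some residual disease as CR, and may miss patients who had no marrow, so it is not a strict upper bound.
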